### **3.7.11. Burden Assessment Scale (BAS)**

Observed values and changes of BAS total score from baseline values will be summarized by treatment group and overall using descriptive statistics. In addition, the BAS will also be summarized by paid or non-paid caregivers.

### **3.7.12. Birchwood Insight Scale (BIS)**

Observed values and changes of each BIS subscale and total score from baseline values will be summarized by treatment group and overall using descriptive statistics.

### **3.7.13. Mini International Neuropsychiatric Interview (M.I.N.I.) Module I & J**

The proportion of subjects with Mini International Neuropsychiatric Interview (M.I.N.I.) Module I (alcohol use disorder) and Module J (substance use disorder) will be summarized by treatment group and overall.

### **3.7.14. Other Assessments**

Caregiver Quality of Life – Burden Dimensions (CarerQOL–7D) and VAS happiness score, and the changes from baseline will be summarized using descriptive statistics as appropriate by treatment group, as well as by paid or non-paid caregivers.

New York Assessment of Adverse Cognitive Effects of Neuropsychiatric Treatment (NY-AACENT) subscales clinician will be summarized for at least one occurrence, each domain. For each domain, the severity, drug related, or functional/role impairment will be summarized. Data from patients and caregiver will be listed only.

Treatment Services Review (TSR-6)-Modified for Mental Health will be listed.

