**Other Assessments**

The following assessments will be collected to explore potential changes in healthcare burden, cognition, insight, and psychosocial care needs:

- Health economics
  - Total healthcare costs as measured by Treatment Services Review (TSR-6) (Modified for Mental Health)
- Functional Assessment
  - Birchwood Insight Scale (BIS)
- Family Measures
  - Caregiver Quality of Life – Burden Dimensions (CarerQOL-7D) and VAS
  - Burden Assessment Scale
- Investigator- and Caregiver-Rated Cognition
  - Respective New York Assessment of Adverse Cognitive Effects of Neuropsychiatric Treatment (NY-AACENT) subscales
- Substance Use
  - Mini International Neuropsychiatric Interview (M.I.N.I.) Module I (alcohol use disorder)
  - Mini International Neuropsychiatric Interview (M.I.N.I.) Module J (substance use disorder)

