### **5.2. Secondary Objectives**

The secondary objectives of this study are to:

- Evaluate quality of life, including daily and social functioning, after treatment with aripiprazole lauroxil
- Characterize the caregiver and healthcare burden

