**Figure 1: Study Design (ALK9072-A401)**

Potential subjects will be evaluated for eligibility according to the inclusion and exclusion criteria at a screening visit and again on Day 1. The first dose of aripiprazole lauroxil will be administered on Day 1. Subjects will receive their first dose of aripiprazole lauroxil no earlier than one week and not later than six weeks following their previous injection of paliperidone palmitate or risperidone. The cross-tapering from risperidone or paliperidone to aripiprazole lauroxil is facilitated by the gradual disappearance of plasma risperidone/paliperidone while aripiprazole is concomitantly released from the initial IM aripiprazole lauroxil injection.

For subjects who have never taken aripiprazole, two test doses of oral aripiprazole 5 mg will be administered during the screening period. Only subjects who exhibit tolerability to oral aripiprazole (either following test doses or by past experience) are eligible to enroll in the study.

On Day 1, qualified subjects will be administered a single IM injection of aripiprazole lauroxil into the gluteal (441, 662 or 882 mg) or deltoid muscle (441 mg), according to the dosing instructions ([Section 8.1](#)). Following the first injection, subjects will return to the study site monthly or every 6 weeks (882 mg, gluteal IM only) for IM aripiprazole lauroxil administration and outpatient assessments. Additional outpatient assessments may be scheduled at the discretion of the investigator.

Efficacy will be evaluated based on Clinical Global Impressions-Severity (CGI-S) and Brief Psychiatric Rating Scale (BPRS) responses.

Safety and tolerability will be evaluated based on adverse events (AEs), injection site reactions (ISRs), clinical laboratory data, vital sign data, Columbia Suicide Severity Rating Scale (C-SSRS) responses, and Abbreviated Extrapyramidal Symptom Rating Scale (ESRS-A) scores. Potential changes in informant-rated cognition, insight, treatment satisfaction, quality of life, daily and social functioning, caregiver and healthcare burden, and psychosocial care needs following a transition to aripiprazole lauroxil will be examined. Total healthcare costs as measured by TSR-6-(Modified for Mental Health) survey will also be evaluated.

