## 12. OTHER ASSESSMENTS

The following assessments will be collected to explore potential changes in healthcare burden, cognition, insight, and psychosocial care needs following a transition to aripiprazole lauroxil:

- Health economics
  - Total healthcare costs as measured by TSR-6-Modified for Mental Health
- Functional Assessment
  - BIS
- Family Measures
  - CarerQOL-7D and VAS
  - Burden Assessment Scale
- Investigator- and Caregiver-Rated Cognition
  - Respective NY-AACENT subscales
- Substance Use
  - M.I.N.I. Module I (alcohol use disorder)
  - M.I.N.I. Module J (substance use disorder)

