#### 1.1.2. Secondary Objectives

[figure not shown]
To evaluate quality of life, including daily and social functioning, after treatment with aripiprazole lauroxil.

To characterize the caregiver and healthcare burden.

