**Figure 1: Study Design (ALK9072-A401)**

Potential subjects will be evaluated for eligibility according to the inclusion and exclusion criteria at a screening visit and again pre-dose on Day 1. The first dose of aripiprazole lauroxil will be administered on Day 1. Subjects will receive their first dose of aripiprazole lauroxil no

earlier than one week and not later than six weeks following their previous injection of paliperidone palmitate or risperidone. The cross-tapering from risperidone or paliperidone to aripiprazole lauroxil is facilitated by the gradual disappearance of plasma risperidone/paliperidone while aripiprazole is concomitantly released from the initial IM aripiprazole lauroxil injection.

For subjects who have never taken aripiprazole, two test doses of oral aripiprazole 5 mg will be administered during the screening period. Only subjects who exhibit tolerability to oral aripiprazole (either following test doses or by past experience) are eligible to enroll in the study.

On Day 1, qualified subjects will be administered a single IM injection of aripiprazole lauroxil into the gluteal (441, 662 or 882 mg) or deltoid (441mg) muscle, according to the dosing instructions. Following the first injection, subjects will return to the study site monthly or every 6 weeks (882 mg only) for IM aripiprazole lauroxil administration and outpatient assessments. Additional outpatient assessments may be scheduled at the discretion of the investigator.

Efficacy will be evaluated based on Clinical Global Impressions-Severity (CGI-S) and Brief Psychiatric Rating Scale (BPRS) responses.

Safety and tolerability will be evaluated based on adverse events (AEs), injection site reactions (ISRs), clinical laboratory data, vital sign data, Columbia Suicide Severity Rating Scale (C-SSRS) responses, and Abbreviated Extrapyramidal Symptom Rating Scale (ESRS-A) scores.

Potential changes in informant-rated cognition, insight, treatment satisfaction, quality of life, daily and social functioning, caregiver and healthcare burden, and psychosocial care needs following a transition to aripiprazole lauroxil will be examined.

The sixth edition of the Treatment Services Review (TSR-6)-Modified for Mental Health survey will also be listed.

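### Healthcare burden is half of a secondary objective, but the SAP only lists its one named measure, the modified TSR-6, and plans no statistic from it

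*SAP*

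**What the plan says.** The secondary objective in protocol 5.2 reads "Characterize the caregiver and healthcare burden", and SAP 1.1.2 repeats it as "To characterize the caregiver and healthcare burden". Protocol Section 12 names one health-economics measure: "Total healthcare costs as measured by TSR-6-Modified for Mental Health". Protocol 7.1 states the intention: "Total healthcare costs as measured by TSR-6-(Modified for Mental Health) survey will also be evaluated". Protocol 14.2 provides descriptive statistics, as a general rule, for variables that are evaluated.

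SAP 1.2 says that changes in "caregiver and healthcare burden, and psychosocial care needs following a transition to aripiprazole lauroxil will be examined". The next sentence of the same section reads "The sixth edition of the Treatment Services Review (TSR-6)-Modified for Mental Health survey will also be listed". SAP 3.7.14 repeats this: "Treatment Services Review (TSR-6)-Modified for Mental Health will be listed".

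Protocol 14.6 and the matching synopsis paragraph name the domains to be summarised under other assessments. Health economics is not among them. SAP Section 5 records no change from the protocol.

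**The concern.** A listing shows each subject's answers but estimates nothing. If the SAP is followed exactly, the study report will contain no figure for inpatient nights, emergency visits or outpatient use, before or after the switch. Healthcare burden could then be described only through a summary designed after the data of an open-label study have been seen. That matters because the choice of items, the scaling to recall length and the choice of baseline can each move the result.

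The word costs raises a second problem. A cost needs a price for each service, and no source of prices is given.

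**Working it through.** **Passages side by side**

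| Step | Healthcare burden | Caregiver burden |
|---|---|---|
| Objective | Protocol 5.2, SAP 1.1.2 | Same |
| Measure | Modified TSR-6 (protocol 12) | Burden Assessment Scale, CarerQOL-7D and VAS (protocol 12) |
| Stated intention | Evaluate costs (protocol 7.1); examine changes (SAP 1.2) | Examine changes (SAP 1.2) |
| Protocol statistics section | Not named in 14.6 | Family measures named in 14.6 |
| SAP analysis | Listing only (1.2, 3.7.14) | Summarised with change from baseline (3.7.11, 3.7.14) |

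The SAP limits the TSR-6 to a listing in two places and summarises it in none. Appendix K of the protocol collects nights, visits, days, sessions and minutes, not money. Neither document gives unit costs or a rule for applying them.

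**The instrument.** Protocol 7.3.15.1 states 22 items. Counting Appendix K: G1 (1) + M1–M5 (5) + P1–P4 (4) + F1–F3 (3) + E1–E5 (5) + L1 (1) + O1–O3 (3) = 22, which agrees. The summary proposed below uses eight of them (M1–M4, P1, P2 through its part 2a, P3, P4) and leaves 22 − 8 = 14 listed.

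**Recall length.** Protocol 7.3.15.1 gives recall of 28 to 42 days. With equal daily use, raw counts at those two lengths differ by 42/28 = 1.5. This is an illustration, not a limit: the form leaves the number of days blank. The Month 1 window in protocol Table 1 opens on Day 22, so recall counted from Day 1 could be 22 − 1 = 21 days.

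**Days at risk.** In Appendix K the medical items after M1 are asked only about days outside a medical hospital, and P2–P4 only about days outside psychiatric inpatient care. For k inpatient nights in a 28-day recall (k is an illustration), the calendar-day rate is (28 − k)/28 of the rate per day at risk:
- k = 7: 21/28 = 0.75
- k = 14: 14/28 = 0.50

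Dividing by calendar days would therefore understate out-of-hospital use most in the subjects who were admitted longest.

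**Sparseness.** The plan has about 50 subjects and three switch-reason groups (SAP 3.1), a mean of 50/3 = 16.7 per group. The documents give no event rates. Assume that 5% to 15% of subjects report any use on a given inpatient or emergency item at a visit:
- Overall: 50 × 0.05 = 2.5 to 50 × 0.15 = 7.5 subjects
- Per group: 16.7 × 0.05 = 0.8 to 16.7 × 0.15 = 2.5 subjects

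At 10%, 5 of 50 has an exact (Clopper-Pearson) 95% interval of 3.3% to 21.8%. The overall column is usable for description; the group columns hardly are.

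**Baseline and visits.** Table 1 schedules the TSR-6 at Screening, Day 1 and every later visit. SAP 3.1 takes the last value before dosing, normally Day 1. Screening lasts up to 30 days. A fixed 28- to 42-day recall at Day 1 can therefore overlap the Screening interview, while recall counted from Screening may be short. Subjects dosed every 6 weeks may skip Months 1 and 4, so the subjects contributing data change from visit to visit.

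**The case against.** The strongest reply is that the SAP follows the protocol's own statistics section. Protocol 14.6 and the synopsis omit health economics from the summarised domains, and protocol Section 12 describes these assessments as exploratory. This stands to the extent that the conflict begins inside the protocol. A reader might infer that the SAP silently dropped a protocol analysis and that its nil entry in Section 5 is wrong. The documents do not settle that, because 7.1 and 14.2 point one way and 14.6 the other. The omission in 14.6 still does not cancel the objective in 5.2 or the statement in 7.1.

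A reader might also infer that SAP 3.1 requires every listed item to be summarised. It does not. It says that summarised data will also be listed, which is the reverse, and SAP 3.7.14 deliberately leaves the patient and caregiver NY-AACENT forms in listings. A listing alone is thus an accepted treatment in this SAP. The case rests on the objective, on protocol 7.1 and on protocol 14.2.

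The mock tables are in a separate document (SAP Section 8) that is not available here and may contain a TSR-6 table. If so, it would go beyond the SAP text, which would still need correcting.

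SAE tables may count admissions as events. They do not give nights, emergency visits without admission or outpatient use, they have no baseline, and neither document designates them as a burden measure.

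**Conclusion.** The point holds as a gap between an objective and its planned analysis, and it should be corrected. As written, the plan yields no statistic for healthcare burden, and total healthcare costs cannot be derived from what the two documents specify.

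The scope is limited. It would be too strong to say that the secondary objective goes unanalysed, since the caregiver half is summarised. The study is uncontrolled and descriptive, and no primary conclusion is affected.

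The 1.5-fold ratio and the 0.75 and 0.50 factors show why scaling and denominators should be fixed in advance; they do not measure bias in a planned result. The expected counts rest on an assumed 5% to 15% of users per item and show only that group-level tables would be sparse.

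**What to change.** In SAP 3.7.14, replace the listing-only sentence with a descriptive TSR-6 summary for all subjects overall. Columns by switch-reason group can be optional.

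1. Report separately: psychiatric inpatient nights (P1), medical inpatient nights (M1), emergency visits (M2), medical outpatient visits (M3, M4), and mental-health day-programme use (P2a), individual sessions (P3) and group sessions (P4). Give the number and percentage of subjects with any use for each. Do not pool P1, M1 and M2 into a composite.
2. Scale counts by the recall days recorded on the form. For the medical items after M1 and for P2–P4, use recall days minus the relevant inpatient nights.
3. State which pre-dose TSR-6 is the baseline and how overlapping or short Day 1 recall is handled. Show n at each visit.
4. Either name a unit-cost source and method, or replace total healthcare costs with healthcare resource use. Record the decision in SAP Section 5 so that protocol 7.1, 12 and 14.6 and the SAP agree.

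The remaining items stay listed. The cost is a few descriptive tables, with sparse counts, and SAP wording. The data, including recall days, are already collected.

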## **4. INTERIM ANALYSES**

Not applicable

## **5. CHANGES IN CONDUCT OR PLANNED ANALYSES FROM THE PROTOCOL**

Not applicable

## **6. DEFINITIONS AND CONVENTIONS FOR HANDLING OF THE DATA**

Dataset specifications will be provided in a separate document.

## **6.1. Analysis Visit Windows**

For all analyses for this study, the scheduled visit and/or time point from the CRF (ie, CRF visit) will be used as the analysis visit and/or time point. There would be one valid value of assessment kept for each scheduled analysis visit in summary/analysis statistics.

Unless specified otherwise, measurements collected from unscheduled visits, will not be included in the summary tables, except for PCS analysis, and will be included in the subject listings.

## **6.2. Safety Data Handling**

All efforts should be made to obtain the missing information from the investigator.

## **6.3. Handling of Partial Dates of Concomitant Medication**

Partial start dates of prior and concomitant medications will be assumed to be the earliest possible date consistent with the partial date. Partial stop dates of concomitant medications will be assumed to be the latest possible date consistent with the partial date. In the case of completely missing stop date, medication will be assumed to be ongoing.

## **7. PROGRAMMING SPECIFICATIONS**

Programming specifications will be provided in a separate document.

## **8. MOCK TABLES, LISTINGS AND GRAPHS (TLGS)**

Mock-up tables and listings will be provided in a separate document.

